8.2.6 MRI

Brain MRI using at least a 1.5-Tesla machine will be performed for the eligible participants at screening to exclude microbleeds, lacunar infarcts, and space-occupying lesions (see Section 5.2, Exclusion criteria) and will include fluid-attenuated inversion recovery (FLAIR) sequence and T2*/gradient echo sequence (GRE). On Days 7 and 57 post dose brain MRI will be performed to confirm absence of brain side effects (e.g., inflammation). In case of clinical findings, CE-MRI may be performed.

Additional brain MRIs must be performed following the onset of a serious CNS adverse event or following a clinically significant worsening of a CNS adverse event. The results should be documented on the appropriate adverse event page and serious adverse event form (if applicable).

MRI data (e.g., images) may be shared with the Sponsor.

[REDACTED]

[REDACTED]

[REDACTED]

[figure not shown]
[REDACTED]

[REDACTED]

[REDACTED]

[REDACTED]

[REDACTED]

8.2.8 Medical History and Demographic Data

Medical history includes clinically significant diseases and all medications (e.g., prescription drugs, OTC drugs, herbal or homeopathic remedies, nutritional supplements) used by the participant within 30 days prior to the screening visit.

Demographic data will include age, sex, and self-reported race/ethnicity.

8.3 ADVERSE EVENTS AND SERIOUS ADVERSE EVENTS

The definitions of an AE or serious adverse event (SAE) can be found in [Appendix 2](#). The non-serious adverse events of special interest and disease-related events and/or disease-related outcomes not qualifying as AEs or SAEs are discussed in Sections [8.3.6](#) and Section [8.3.7](#).

The Investigator and any qualified designees are responsible for ensuring that all adverse events (including assessment of seriousness, severity and causality; see [Appendix 2](#)) are recorded on the Adverse Event eCRF and reported to the Sponsor in accordance with instructions provided in this section and in [Appendix 2](#).

Procedures used for recording adverse events are provided in [Appendix 3](#).

8.3.1 Time Period and Frequency for Collecting Adverse Event and Serious Adverse Event Information

The method of recording, evaluating, and assessing causality of AEs and SAEs and the procedures for completing and transmitting SAE reports are provided in [Appendix 2](#).

Clinic staff will seek information on adverse events at each study day. All adverse events, whether reported by the participant or noted by study personnel, will be recorded in the participant's medical record and on the Adverse Event eCRF as follows:

After informed consent has been obtained **but prior to initiation of study treatment**, all adverse events caused by a protocol-mandated intervention should be reported (e.g., adverse events related to invasive procedures such as lumbar puncture). If the adverse event meets the criteria for serious adverse event (see Section 2 from [Appendix 2](#)), it should be reported immediately.

After initiation of study treatment, all adverse events, regardless of relationship to study treatment, will be reported until the last follow-up visit (57 ± 4 days after dosing).

Post-study adverse events and serious adverse events: The Investigator is not required to actively monitor participants for adverse events after the end of the adverse event reporting period of 57 days ± 4 days after dosing.

However, if the Investigator learns of any SAE (including a death) or other adverse events of concern that are believed to be related to prior treatment with study treatment, at any time after a participant has been discharged from the study, and the Investigator considers the event to be reasonably related to the study treatment or study participation, the Investigator must promptly notify the Sponsor. For the procedure of reporting, see [Appendix 2](#).

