- c) Includes single measurements of systolic and diastolic blood pressure, pulse rate and body temperature. All measurements to be taken after the participant has rested in a supine position for at least 5 minutes.
- d) Triplicate 12-lead ECGs (within 5 minutes) will be measured after the participant has rested in a supine position for at least 10 minutes.
- e) Dipstick analysis of protein, blood, glucose, pH and leukocytes.
- f) Hepatitis B, C, HIV 1 and 2.

Table 1 Overall Schedule of Activities (cont.)

- g) Participants will have to be fasted (water consumption is permitted) for at least 10 hours prior to full panel biochemistry laboratory safety tests (with the exception of screening and follow-up where a fasting period of 4 hours is sufficient). On Day 1, no food is permitted from 2 hours prior to dosing until 4 hours after start of the infusion. On all other days of the in-house period, standard breakfast, lunch, dinner and snack will be provided up to discharge, at the times deemed convenient by the clinical site.
- h) Intensity of adverse events will be graded on a five-point scale (Grade 1, Grade 2, Grade 3, Grade 4 and Grade 5) based on the NCI CTCAE (v5), which can be found at:
https://ctep.cancer.gov/protocoldevelopment/electronic_applications/docs/CTCAE_v5_Quick_Reference_8.5x11.pdf
- i) The Sponsor may decide to terminate PK sampling earlier and/or timing of PK sampling may be modified based on emerging PK data (e.g., consecutive postdose PK samples with below the limit of quantification [BLQ] concentration).
- j) Respiratory rate to be measured after the participant has rested in a supine position for at least 5 minutes.

█ [REDACTED]

█ [REDACTED]

[REDACTED]

█ [REDACTED]

- o) Participants will be randomized to two subgroups per dose group. One subgroup will have the CSF sampling on Day 3, the other subgroup on Day 5. The safety biomarker (blood) and coagulation sample will be taken accordingly.
- p) In case of ADA positive results at follow-up visit, the participant will be asked to come back to the unit monthly for additional ADA testing until *this is no longer clinically indicated (see Section 8.7)*. At each visit a corresponding PK sample must be also taken.

Table 1 Overall Schedule of Activities (cont.)

■	[REDACTED]
■	[REDACTED]
■	[REDACTED]
■	[REDACTED]
■	[REDACTED]

Table 2 Specific Schedule of Assessments

Procedure	Day -2	Day -1	Day 1												Day 2
			Nominal Time												

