4.4 END OF STUDY DEFINITION

The end of the study is defined as the date when the last participant last observation (LPLO) occurs. LPLO is expected to occur 57 ± 4 days after last dose administration.

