8.7 IMMUNOGENICITY ASSESSMENTS

As RO7126209 is a bispecific monoclonal antibody there is a risk that ADA against RO7126209 could develop, potentially reducing its efficacy and/or potentially resulting in symptomatic hypersensitivity reaction, including immune-complex reactions. Antibodies to RO7126209 will be evaluated in blood samples collected from all participants according to the SoA (Section 1.3). ADA data will not be required for dose escalation decisions.

[REDACTED]

[REDACTED]

[REDACTED]. The date and time of each sample will be recorded in the eCRF.

[REDACTED]

The blood samples will be destroyed 6 months after the release of final bioanalytical report at the CRO performing the analysis or shipped to Roche. In the latter case the samples may be stored up to 2 years after the date of final CSR. Details on sampling procedures, sample storage and shipment are given in the sample documentation.
Details on sampling procedures, sample storage and shipment are described in the sample documentation.

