9.3.5 Immunogenicity Analyses

The immunogenicity analyses will include all participants with at least one ADA assessment, irrespective of whether or not the participant receives any treatment ([Shankar et al 2014](#)).

The numbers and proportions of ADA-positive participants and ADA-negative participants at baseline (baseline prevalence) and after study drug administration (post-baseline incidence during both the treatment and follow-up periods) will be summarized.

- Participants are considered to be ADA positive if they are ADA negative at baseline but develop an ADA response following study drug administration (treatment-induced ADA response), or if they are ADA positive at baseline and the titer of one or more post-baseline samples is greater than the titer of the baseline sample by a scientifically reasonable margin such as at least 4-fold (treatment-enhanced ADA response).

- Participants are considered to be ADA negative if they are ADA negative at baseline and all post-baseline samples are negative, or if they are ADA positive at baseline but do not have any post-baseline samples with a titer that is greater than the titer of the baseline sample by a scientifically reasonable margin such as at least 4-fold (treatment unaffected).

The relationship between ADA status and safety, efficacy, PK, and biomarker endpoints will be analyzed and reported descriptively via subgroup analyses.

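### Participants who are ADA positive at Day 57 return monthly for ADA and PK sampling, but the readable text provides no systematic collection of new adverse events at those visits

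*Combined protocol and SAP*

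**What the plan says.** **The extension.** Table 1 footnote p (Section 1.3): "In case of ADA positive results at follow-up visit, the participant will be asked to come back to the unit monthly for additional ADA testing". It adds "At each visit a corresponding PK sample must be also taken". The visits continue until they are no longer clinically indicated, with a pointer to Section 8.7. No adverse event (AE) query is listed for them.

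**The hazard.** Section 8.7 describes ADA as "potentially resulting in symptomatic hypersensitivity reaction, including immune-complex reactions". Parts of that section are redacted.

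**The AE window.** Section 8.3.1 states that, once treatment has started, "all adverse events, regardless of relationship to study treatment, will be reported until the last follow-up visit (57 ± 4 days after dosing"). It then says "The Investigator is not required to actively monitor participants for adverse events after the end of the adverse event reporting period", which it again puts at 57 ± 4 days.

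**What continues afterwards.** The next paragraph of Section 8.3.1 requires prompt notification, at any time, of SAEs or other AEs of concern that the investigator learns of and considers related. Sections 8.3.3.1 and 8.10.5 keep AEs already reported under follow-up until they resolve, stabilise or are explained.

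**The analysis.** Section 9.3.5: "The relationship between ADA status and safety, efficacy, PK, and biomarker endpoints will be analyzed and reported descriptively via subgroup analyses". Table 9 in Section 9.2 carries a similar sentence. Neither gives a time window.

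**End of study.** Section 4.4: "LPLO is expected to occur 57 ± 4 days after last dose administration". The monthly visits are not mentioned.

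**The concern.** The extension exists because persisting ADA may have clinical consequences, yet the two assessments it specifies are laboratory samples. A participant first found positive at Day 57 has all later observation outside the AE window. If a rash, fever or joint pain then appears and is neither serious nor judged related and of concern, the readable protocol does not require anyone to ask about it or to record it.

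At stake is the reading of the ADA-by-safety description in a first-in-human study. A lack of late non-serious events in ADA-positive participants could reflect how events were sought rather than whether they occurred, and the report would not let a reader tell which. Whether data after Day 57 enter that description at all is also unstated.

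**Working it through.** The check is mainly a comparison of rules, with a little arithmetic on timing and numbers.

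**1. Planned numbers (Sections 4.1 and 9.1).** Five cohorts: two of at least 4 active + 2 placebo and three of at least 6 active + 2 placebo.
- Active: 2 × 4 + 3 × 6 = 26
- Placebo: 2 × 2 + 3 × 2 = 10
- Total: 26 + 10 = 36, which reproduces the protocol's expected enrolment.

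**2. Timing.** Routine AE reporting ends between Day 57 − 4 = 53 and Day 57 + 4 = 61. Assume that monthly means 28 to 31 days after the follow-up visit.
- Earliest first extension visit: 53 + 28 = Day 81
- Latest first extension visit: 61 + 31 = Day 92

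On that assumption every extension visit falls outside the routine AE window.

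**3. Which late events have a route to the sponsor?**

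| Event after the Day 57 visit | Rule that applies | Captured? |
|---|---|---|
| AE with onset before Day 57, still open | 8.3.3.1, 8.10.5 | Yes, followed to outcome |
| New SAE believed related | 8.3.1 post-study paragraph; Appendix 2 Section 5.1 | Yes, if the investigator learns of it |
| New non-serious AE of concern, believed related | 8.3.1 post-study paragraph | Notified if learned of, but the post-study text of Appendix 2 Section 5.1, to which 8.3.1 refers for procedure, covers only serious related events |
| New non-serious AE, not judged related or not of concern | None in the readable text | No requirement |

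The second and third rows are passive and depend on a causality judgement. The fourth has no route.

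**4. Are sites told to ask?** Section 8.3.1 has staff seek AEs on every study day, and Section 8.3.2 wants consistent questioning at every time-point where participants are evaluated. Whether a footnote p visit counts as either is not stated. The fixed end of the reporting period points towards no; the general wording could be read as yes. Two sites, or two members of staff, could reasonably differ.

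**5. How many participants?** The documents give no ADA rate. For assumed rates among the 26 active participants:
- 5%: 26 × 0.05 = 1.3
- 20%: 26 × 0.20 = 5.2
- 40%: 26 × 0.40 = 10.4

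A placebo participant who tested positive would also enter the extension, so these are not upper limits.

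**6. Could there be anything to miss?** With k participants in the extension and an assumed late-AE risk p each, from any cause, the chance of at least one late AE is 1 − (1 − p)^k.
- k = 3, p = 0.05: 1 − 0.95³ = 0.143
- k = 6, p = 0.10: 1 − 0.90⁶ = 0.469
- k = 13, p = 0.20: 1 − 0.80¹³ = 0.945

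Both inputs are assumptions. The range shows only that the question is not empty.

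**The case against.** **The site is not forbidden to ask.** Section 8.3.1 removes a duty to monitor actively; it does not say that AEs must not be sought. Together with the general wording in Sections 8.3.1 and 8.3.2, a site might well ask. This stands: the instruction is ambiguous, not prohibitive. Ambiguity still means uneven ascertainment.

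**Collection does not stop altogether.** A reader might infer that the extension cannot inform the ADA-safety description at all, or that an empty late-event table would mean that nothing was collected. The documents do not support that. Related SAEs and related AEs of concern are notified without time limit, and open AEs are followed, so later ADA and PK results can be read against both. What is lost is a systematic view of new events.

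**Redaction.** Footnote p points to Section 8.7, part of which is blacked out and may hold rules for these visits. This stands as a caveat. Even so, Section 8.3.1 is worded without exception and would need a cross-reference.

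**Section 4.4 does not conflict.** A reader might infer that the expected last observation contradicts the extension. It does not: end of study is defined as the date when the last observation occurs, and Day 57 ± 4 is only when that is expected. A clarifying clause is enough.

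**Limited gain.** Only ADA-positive participants are followed, so no concurrent ADA-negative or placebo comparison results. An open question also finds symptoms, not silent laboratory changes. Both points stand. The planned analysis is descriptive in any case, and the immunogenicity endpoint, ADA incidence, is unaffected.

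**Conclusion.** The point holds in this form: the readable protocol does not provide for systematic collection of new AEs, especially non-serious ones, at the monthly visits of participants who are ADA positive at Day 57. The extension therefore cannot support a systematic assessment of new late AEs in that group.

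The gap affects everyone who enters the extension, for its whole length. The number is unknown; the 1 to 10 active participants in the working rest on assumed ADA rates. The conclusion also assumes that the redacted part of Section 8.7 does not already require AE questioning, and that monthly means about four weeks. The change is worth making because the named hazard and the visits already coincide, but the resulting data would be descriptive only.

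**What to change.** 1. In Section 8.3.1 and Appendix 2 Section 5.1, state that for participants returning under footnote p the AE reporting period runs to their last ADA visit. Cross-refer to any relevant rule in Section 8.7.
2. Add to footnote p that the standard open AE question is asked at each such visit and the answer is recorded on the AE eCRF.
3. In Section 9.3.5, say how data after Day 57 are used. List or tabulate AEs with onset after the Day 57 visit separately and descriptively, apart from the main incidence table, because ADA-negative participants have no matching follow-up.
4. In Section 4.4, note that the expected last observation may be later if footnote p visits take place.

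**Cost.** A wording amendment and one question at visits that already take place. Database closure would wait for the last ADA visit, or late events would go into an addendum.

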8.3.2 Method of Detecting Adverse Events and Serious Adverse Events

Care will be taken not to introduce bias when detecting AEs and/or SAEs. Open-ended and non-leading verbal questioning of the participant is the preferred method to inquire about AE occurrence.

A consistent methodology of non-directive questioning should be adopted for eliciting adverse event information at all participant evaluation time-points.

8.3.3 Follow-Up of Adverse Events and Serious Adverse Events

8.3.3.1 Investigator Follow-Up

The Investigator should follow each adverse event until the event has resolved to baseline grade or better, the event is assessed as stable by the Investigator, the event is otherwise explained, the participant is lost to follow-up (Section 7.3), or the participant withdraws consent. Every effort should be made to follow all serious adverse events considered to be related to study treatment or trial-related procedures until a final outcome can be reported.

During the study period, resolution of adverse events (with dates) should be documented on the Adverse Event eCRF and in the participant's medical record to facilitate source

data verification. If, after follow-up, return to baseline status or stabilization cannot be established, an explanation should be recorded on the Adverse Event eCRF.

All pregnancies reported during the study should be followed until pregnancy outcome and reported according to the instructions provided in Section [8.3.5](#).

8.3.3.2 Sponsor Follow-Up

For serious adverse events, non-serious adverse events of special interest, and pregnancies, the Sponsor or a designee may follow-up by telephone, fax, electronic mail, and/or a monitoring visit to obtain additional case details and outcome information (e.g., from hospital discharge summaries, consultant reports, autopsy reports) in order to perform an independent medical assessment of the reported case.

8.3.4 Regulatory Reporting Requirements for Serious Adverse Events

Prompt notification by the Investigator to the Sponsor of a SAE is essential so that legal obligations and ethical responsibilities towards the safety of participants and the safety of a study treatment under clinical investigation are met.

The Sponsor has a legal responsibility to notify both the local regulatory authority and other regulatory agencies about the safety of a study treatment under clinical investigation. The Sponsor will comply with country-specific regulatory requirements relating to safety reporting to the regulatory authority, Institutional Review Boards (IRB)/Independent Ethics Committees (IEC), and investigators.

Investigator safety reports must be prepared for suspected unexpected serious adverse reactions (SUSAR) according to local regulatory requirements and Sponsor policy and forwarded to investigators as necessary.

An investigator who receives an investigator safety report describing a SAE or other specific safety information (e.g., summary or listing of SAEs) from the Sponsor will review and then, file it along with the IB and will notify the IRB/IEC, if appropriate according to local requirements.

For immediate and expedited reporting requirements from Investigator to Sponsor and from Sponsor to Health Authority, investigators, IRB and EC, see [Appendix 2](#).

8.3.4.1 Emergency Medical Contacts

To ensure the safety of study participants, access to the Medical Monitors is available 24 hours a day 7 days a week. Medical Monitors' contact details will be available on a separate list generated by the study management team.

8.3.5 Pregnancy

Male participants will be instructed through the Informed Consent Form to immediately inform the Investigator if their partner becomes pregnant during the study or within 57 ± 4 days after dosing.

If a pregnancy is reported, the Investigator should inform the Sponsor within 24 hours of learning of the pregnancy and should follow the pregnancy reporting process as detailed in [Appendix 5](#).

Abnormal pregnancy outcomes (e.g., spontaneous abortion, fetal death, stillbirth, congenital anomalies, ectopic pregnancy) are considered SAEs ([Appendix 5](#)).

8.3.6 Non-Serious Adverse Events of Special Interest

Non-serious adverse events of special interest are required to be reported by the Investigator to the Sponsor immediately (i.e., no more than 24 hours after learning of the event; see [Appendix 2](#) for reporting instructions).

Non-serious adverse events of special interest for this study include the following:

- Cases of an elevated ALT or AST in combination with either an elevated bilirubin or clinical jaundice, as defined in [Appendix 3](#).
- Suspected transmission of an infectious agent by the study treatment, as defined below:

Any organism, virus, or infectious particle (e.g., prion protein transmitting transmissible spongiform encephalopathy), pathogenic or non-pathogenic, is considered an infectious agent. A transmission of an infectious agent may be suspected from clinical symptoms or laboratory findings that indicate an infection in a patient exposed to a medicinal product. This term applies only when a contamination of the study treatment is suspected.

8.3.7 Management of Specific Adverse Events

IRRs as defined by Kang and Saif (2007) are “any signs or symptoms experienced by patients during the infusion of pharmacologic or biologic agents or any event occurring on the first day of drug administration”. IRRs are common adverse drug reactions (ADRs) reported with the use of biologic therapies. IRRs are usually reported with the first or second infusion of a therapeutic monoclonal antibody and tend to be dose-related. Such reactions typically occur during or shortly after an infusion or within 24 hours after study drug infusion. IRRs is a basket term including other terms such as anaphylaxis, anaphylactoid reactions, complement activation-related pseudoallergy (CARPA) and cytokine release syndrome. Combinations of IRR types may occur in the same patient ([Doesseger et al 2015](#)).

IRR symptoms may be indistinguishable from an anaphylaxis Type 1 hypersensitivity reaction (i.e., flushing, rash, respiratory difficulty, hypotension, tachycardia); however,

hypersensitivity reactions (IgE-mediated) generally do not occur with the first exposure to a biologic therapy.

Anaphylactoid reactions may occur with the first exposure to an antigen and may be clinically indistinguishable from anaphylaxis. Unlike anaphylactic reactions, anaphylactoid reactions are milder upon repeated administration.

CARPA typically occurs within minutes after starting the infusion. However, it may be delayed, particularly in premedicated patients. The most frequent symptoms being flushing, rash, dyspnea, chest pain, back pain and subjective distress.

Cytokines release syndrome (CRS) can present as with a variety of symptoms ranging from mild, flu-like symptoms (fever, fatigue, headache, rash, arthralgia, and myalgia) to more severe cases characterized by hypotension as well as high fever and can progress to an uncontrolled systemic inflammatory response with vasopressor-requiring circulatory shock, vascular leakage, disseminated intravascular coagulation, and multi-organ system failure. Laboratory abnormalities that are common in patients with CRS include cytopenias, elevated creatinine and liver enzymes, deranged coagulation parameters, and a high C-reactive protein (CRP) ([Shimabukuro-Vornhagen et al 2018](#)).

[Figure 2](#) describes the process for the overall evaluation of AEs to determine whether an AE is an IRR.

Figure 2 Evaluation and Reporting of Infusion Related Reaction (IRR)

[figure not shown]

Figure 2 Evaluation and Reporting of Infusion Related Reaction (IRR) (cont.)

1. Source: [Lee et al 2014](#).

NCI CTCAE = National Cancer Institute Common Terminology Criteria for Adverse Events.

Note: Based on the NCI CTCAE (v5), which can be found at:

https://ctep.cancer.gov/protocoldevelopment/electronic_applications/docs/CTCAE_v5_Quick_Reference_8.5x11.pdf

2. Note: High-Dose Vasopressor (duration ≥ 3 hours) in table below

Pressor	Dose
Norepinephrine monotherapy	≥ 20 mcg/min
Dopamine monotherapy	≥ 10 mcg/kg/min
Phenylephrine monotherapy	≥ 200 mcg/min
Epinephrine monotherapy	≥ 10 mcg/min
If on vasopressin	Vasopressin + norepinephrine equivalent of ≥ 10 mcg/min ^a
If on combination vasopressors (not vasopressin)	Norepinephrine equivalent of ≥ 20 mcg/min ^a

Source: [Russell et al 2008](#).

mcg =microgram; min =minute; VASST =Vasopressin and Septic Shock Trial.

^a VASST vasopressor equivalent equation: norepinephrine equivalent dose = [norepinephrine (mcg/min)] + [dopamine (mcg/kg/min)] + [phenylephrine (mcg/min) $\div 10$].

Specific management steps for IRRs and hypersensitivity reactions of different severity are provided in [Table 7](#). The participant should be monitored until complete resolution of the symptoms and treated as clinically indicated.

A blood sample will be taken in all participants at baseline (predose Day 1) and 6 hours post dose (the timing might be adjusted based on emerging data) [REDACTED]. In case a Grade ≥ 3 IRR occurs, blood samples for the assessment [REDACTED] will be collected and analysed along with the paired baseline sample. The baseline and 6-hour (timing might be adjusted based on emerging data) post dose samples of all participants will be analysed to assess the relationship between dose, cytokine release and occurrence of IRRs as appropriate. Guidelines for managing infusion-related reactions with onset after infusion but within 24-hour window in presented in [Table 8](#)

Table 7 Guidelines for Managing Infusion-Related Reactions with onset during infusion

Event	Action to Be Taken
Grade 1	Stop or slow down study drug infusion to 50% of the initial rate. Assess vital signs. Clinical observation for improvement/resolution of symptoms. No treatment is needed.
Grade 2	Stop study drug infusion. Perform serial vital signs assessment every 15 minutes, supportive therapy (fluids [Normal Saline or Lactated Ringers], supplemental oxygen, diphenhydramine 25–50mg PO or IV Q6h for rash, acetaminophen 650 mg PO [or minimum recommended adult dose of paracetamol]) Q6h. ADA and PK levels should be drawn. If symptoms resolve completely during the visit, infusion may resume at 50% of the previous infusion rate.
Grade 3	Stop study drug infusion. Perform serial vital signs assessment as dictated by the patient’s clinical symptoms, supportive therapy (fluids [Normal Saline or Lactated Ringers], supplemental oxygen, diphenhydramine 25–50mg PO or IV for rash, acetaminophen 650 mg PO [or minimum recommended adult dose of paracetamol], methylprednisolone 125 mg IV). Labs: [REDACTED] within 3 hours of the event and to be repeated in 48–72 hours post event. ADA and PK levels should be drawn.
Grade 4	Stop study drug infusion. Perform serial vital signs assessment every 5 minutes, supportive therapy (fluids [Normal Saline or Lactated Ringers], supplemental oxygen/ intubation and ventilatory support, diphenhydramine 25–50 mg PO or IV for rash, acetaminophen 650 mg PO [or minimum recommended adult dose of paracetamol], methylprednisolone 125 mg IV). Labs: [REDACTED] within 3 hours of the event and to be repeated in 48–72 hours post event. ADA and PK levels should be drawn.
Anaphylaxis	Stop study drug infusion. Assess vital signs every 5 minutes. Administer IV fluids (Normal saline or Lactated Ringers), supplemental oxygen/ventilatory support, for systemic symptoms (angioedema, bronchospasm) epinephrine 1:1000, 0.3 mL subcutaneous (may be repeated in 20 minutes; in patients on beta blockers, glucagon administration may be needed), diphenhydramine 25–50 mg IV, methylprednisolone 125 mg IV). Labs: [REDACTED] within 3 hours of the event and to be repeated in 48–72 hours post-event. Discontinue participants from the study. ADA and PK levels should be drawn (See Lieberman et al 2015 for anaphylaxis guidance).

Table 8 Guidelines for Managing Infusion-Related Reactions with onset after infusion but within 24-hour window

Event	Action to Be Taken
Grade 1	
 • Treat symptomatically as indicated, including antihistamines, antipyretics, and/or analgesics as needed. • Treat fever and neutropenia if present. • Monitor fluid balance; administer IV fluids as clinically indicated.
Grade 2	
 • Follow all Grade 1 recommendations. • Monitor cardiac and other organ function closely. • Hemodynamic support as indicated. • Oxygen for hypoxia. • Admit to ICU as appropriate. • If no improvement within 24 hours: 
 – Notify Medical Monitor. – Consider administering tocilizumab 8 mg/kg e IV as a single dose. • ADA and PK levels should be drawn.
Grade 3	
 • Notify Medical Monitor. • Cardiopulmonary and organ function monitoring in Intensive Care Unit. • Hemodynamic support as indicated. • Oxygen for hypoxia. • Other supportive care as clinically indicated (e.g., fever and neutropenia, infection). • Administer tocilizumab 8 mg/kg IV. 
 – If no clinical improvement within 24 hours: Administer repeat dose of tocilizumab 8 mg/kg. Consider initiating IV corticosteroids (e.g., methylprednisolone [2 mg/kg/day] or dexamethasone 10 mg for neurologic symptoms). • Labs: [REDACTED] within 3 hours of the event and to be repeated in 48 - 72 hours post event. ADA and PK levels should be drawn.
Grade 4	
 • Follow all Grade 3 management guidelines Labs: [REDACTED] within 3 hours of the event and to be repeated in 48 – 72 hours post event. ADA and PK levels should be drawn.

In case of signs/symptoms of IRR in the sentinel cohort, IRR risk mitigation steps may be implemented in the remaining participants of the dose level and the higher dose levels. The same approach will applied in case of signs/symptoms of IRRs in the

participants enrolled in the main cohort at a certain dose level for the higher dose levels. In order to reduce the occurrence and potential impact of IRRs, slower infusion time may be applied to all participants of the cohort (and the cohorts at higher dose level), after discussion and approval by the medical monitor.

